6 STUDY DESIGN AND TREATMENT PLAN

In this Phase 1, open-label, multi-center study, subjects with persistent, metastatic or recurrent squamous cell or non-squamous cell carcinoma, adenosquamous carcinoma, or adenocarcinoma of the cervix who have failed conventional therapy will receive the highest dose tolerated of ADXS11-001 infused intravenously (IV)

(± 10 minutes) with overall infusion volume of 250 mL on Day 1 of Weeks 1, 4, 7, and 10 of each 12-week cycle. Subjects must complete the prophylactic regimen at least prior to each ADXS11-001 infusion (as noted in Section 11.1) to mitigate and manage the potential immune response seen with immunotherapy administration.

Subjects who experience a DLT during the dose escalation portion of the study or experience events described as a DLT in any subsequent treatment cycle will be discontinued from study treatment. However, if the subject who experienced a DLT shows significant response to ADXS11-001, they may be eligible to receive ADXS11-001 at a lower dose level for subsequent doses and cycles following discussion and agreement between the Investigator and Sponsor. See Section 6.1 Dose Limiting Toxicity Criteria for definition of DLT.

The treatment to be used in this trial is outlined below in Table 4. Trial treatment should begin on the day of randomization or as close as possible to the date on which the treatment level is allocated/assigned.

Details on the dose calculation, preparation and administration are provided in the Pharmacy Manual.

Table 4 Trial Treatment

[figure not shown]
Dose Level	ADX11-001	Schedule
1	5 x 10 ⁹ CFU	Q3wks
2	$1 \times 10^{10} \text{CFU}$	Q3wks
-1	$1 \times 10^9 \text{CFU}$	Q3wks

ADXS11-001 will be given as a 3 weeks in repeating 12-week cycles

250 mL IV infusion every

A standard 3 + 3 design will be used in the dose escalation portion of the study. ADXS11-001 will be administered in sequential cohorts of 3-6 subjects, with a minimum of 48 hours between initial dosing for each of the first 3 subjects treated at each dose level. The first cohort will enroll a minimum of 3 subjects, according to a standard 3 + 3 design shown schematically in Figure 1.

Figure 1 3+3 Design Schematic

- Subjects in the first cohort will receive a dose of ADXS11-001 5 x 10⁹ CFU (Dose Level 1).
- If no DLTs are experienced in the 28 day DLT observation period at Dose Level 1, the next dose level of ADXS11-001 1 x 10¹⁰ CFU (Dose Level 2) will be explored.
- If 1 DLT is experienced at Dose Level 2 (ADXS1-001 1 x 10¹⁰ CFU), then 3 additional subjects will be enrolled at that same dose level. If there is 1 DLT among the 6 subjects, then the Dose Level 2 may be identified as the RP2D and will be expanded to further define safety and efficacy.
- If \geq 2 DLTs are observed within 28 days of dosing for subjects in the first dose cohort, the starting dose of ADXS11-001 will be de-escalated to 1 x 10⁹ CFU and a dose de-escalation cohort may be enrolled (Dose Level -1).

All decisions regarding dose level escalation or de-escalation will be guided by the 3 + 3 study design and will be made by the Sponsor in consultation with the Investigator(s).

The RP2D will be selected based on an observed DLT rate of <33%. The Sponsor reserves the right to expand the number of subjects in each of the cohorts to better evaluate safety and tolerability. Cohorts will be expanded in groups of 3 subjects.

Following identification of the RP2D, additional subjects may be enrolled into the expansion cohort to allow approximately 15 subjects to be treated at that dose level. All subjects in the Dose Expansion Cohort may be enrolled simultaneously.

DLTs will only be assessed during the first 28 days in cycle 1 (See Section 6.1, Dose Limiting Toxicity Criteria, for DLT definition). Transient hypotension which may require IV fluids for management is an expected event that subjects may experience with ADXS11-001 infusions. Subjects with signs of cytokine release symptoms ≥Grade 3 (per CTCAE v 4.03) that persist for more than 24 hours despite symptomatic treatment, will be judged to have a DLT. Blood cultures will not be obtained on a routine basis but will be collected in subjects who have persistent fever 24 hours after the end of ADXS11-001 infusion. Subjects will receive a 7-day course of either oral 80 mg trimethoprim / 400 mg sulfamethoxazole once daily or 160 mg trimethoprim / 800 mg sulfamethoxazole (DS) 3 times over the course of the 7 days. Subjects with known allergy to sulfa drugs may receive ampicillin 500 mg 4 times daily for 7 days beginning on Day 4 (approximately 72) hours) after each study treatment infusion. A subject who experiences a fever (CTCAE Grade 1 or greater) 24 hours following the completion of ADXS11-001 infusion should be started on NSAIDS, hydration and other appropriate measures to treat the fever. In the event that the fever persists or worsens 48 hours following the completion of ADXS11-001 infusion then oral or broad spectrum IV antibiotics should be considered based on the subject's medical condition. If the fever remains unresponsive to oral/IV antibiotics 72 hours following the completion of the infusion then a blood culture should be obtained to evaluate for listeremia and determine the appropriate treatment course for the subject. Study cycles can be repeated at the RP2D (or less) for each subject until a discontinuation criterion is met. Criteria include documented disease progression, intolerable side effects not resolved with dose reduction or change in pre-medications, or the completion of 1 cycle of treatment post observation of complete response per RECIST 1.1 and immunerelated RECIST criteria (irCR).

Safety will be assessed by comparing treatment-related AEs, changes in physical examinations, vital sign measurements, and laboratory abnormalities.

Immunologic effects will be measured and evaluated by collection of peripheral blood for preparation of peripheral blood mononuclear cells (PBMCs) and serum immediately prior to each ADXS11-001 infusion and 2 weeks after every ADXS11-001 infusion in Cycle 1 only (Day 1 of Weeks 3, 6, 9, and 12). PBMCs will be analyzed for the presence and quantitation of HPV-E7 and HPV-E6 specific CD8+ T-cells through ELISpot and other assays as well as Treg cells and MDSCs. PBMC immunologic gene expression analysis may also be conducted. Serum will be evaluated for serum cytokines, chemokines, and other potential markers. Blood will be collected in Cycle 1 only at 3 time points immediately prior to each ADXS11-001 infusion and 2 hours and 4 hours post infusion (±15 minutes- Day 1 of Weeks 1, 4, 7, and 10).

Subjects should arrive at the study center on the days of their scheduled ADXS11-001 administration in order to be evaluated, have laboratory specimens collected before treatment commences, and complete the study prophylactic regimen at least pre-infusion before receiving the ADXS11-001 infusion.

Subjects will remain at the study site for a minimum of 4 hours after the infusion for safety observations, and if necessary treatment of side effects resulting from the study treatment administration. Treatment and observation of side effects may take up to an additional 4 hours, so subject arrival at the study center should be early enough to accommodate a possible 9-hour visit day. Vital signs will be taken pre-dose then every after the infusion as a safety measure.

After the initial study cycle, subjects who respond or have immune-related SD at or after tumor assessments may receive additional treatment at the same dose and schedule, until either evidence of disease progression, intolerable side effects not resolved with dose reduction or change in premedications, or for 1 completed study cycle post achievement of CR per RECIST 1.1 and immune-related RECIST criteria (irCR). These subjects may continue to be evaluated for response every 12 weeks.

Study treatment will be modified as per Table 11 in Section 11.6.1 Treatment Modification Guidelines.

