Doses will be escalated in the standard 3 + 3 fashion, starting with 5 x 10^9 colony forming units (CFU) to a maximum dose level of 1 x 10^{10} CFU. Dose cohorts of 3 subjects each will be treated. In the absence of dose-limiting toxicity (DLT) as defined in Section 6.1 Dose Limiting Toxicity assessed during the first treatment cycle, the dose will be escalated to the next dose level for the next 3 subjects. If DLT is seen in 1 of 3 subjects, another 3 subjects will be treated at that same dose. If DLT is seen in 2 of 6 subjects, then that dose level will be considered maximum tolerated dose (MTD) and the previous dose level will be selected as the recommended Phase 2 dose (RP2D). The RP2D will be selected based on an observed DLT rate of < 33%.

Treatment cycles can be repeated at the RP2D (or less) for an individual subject until a discontinuation criterion is met. Discontinuation criteria include documented disease progression, intolerable side effects not resolved with dose reduction or change in premedications or the subject completes 1 cycle of treatment post observation of complete response (CR) per RECIST 1.1 and immune-related RECIST criteria (irCR).

Sponsor:	Name of Finished Product:	Type of Treatment:
Advaxis, Inc.	ADXS11-001	Lm-LLO Immunotherapy

Further assessment of the RP2D level may be explored in an expansion cohort in subjects with persistent, metastatic, or recurrent carcinoma of the cervix who have failed conventional therapy to evaluate the safety and clinical activity of ADXS11-001. Treatment will continue for each subject until a discontinuation criterion is met. The end of treatment will be defined as 1 year after the last subject's first treatment or until that subject has met a discontinuation criterion. All subjects will be followed for adverse events (AEs) and serious adverse events (SAEs) from the time written informed consent is signed through the completion of the *Lm* surveillance period.

Safety will be assessed by comparing treatment-related AEs, changes in physical examinations, vital sign measurements, laboratory abnormalities and *Lm* surveillance monitoring.

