6.1 Dose Limiting Toxicity Criteria

DLT will be evaluated during the first 28 days of the first cycle during the dose escalation portion of the trial. All toxicities will be graded using CTCAE v 4.03. The occurrence of any of the following toxicities will be considered a DLT, if judged by the Investigator to be possibly, probably or definitely related to therapy. Treatment modifications for DLT are shown in Table 11.

Hematologic:

- 1. Grade 4 hematologic toxicity.
- 2. Febrile Neutropenia, defined as absolute neutrophil count (ANC) < 1000/mm³ with a single temperature of >38.3° C (101° F) or a sustained temperature of >38° C (100.4° F) for more than 1 hour.
- 3. Grade 3 thrombocytopenia lasting >72 hours.
- 4. Grade 4 thrombocytopenia.

Non-Hematologic:

1. ≥Grade 3 non-hematologic toxicity, (excluding nausea, vomiting and/or diarrhea lasting <3 days and reversible with medical intervention).

- 2. Grade 3 non hematologic laboratory values, (excluding transient Grade 3 laboratory value abnormalities, hematologic and non-hematologic, reversible within 5 days and without necessity for medical intervention).
- 3. Listeremia: positive blood cultures(s) along with persistent (for 72 hours post dose) symptoms consistent with listeremia (e.g., fever and muscle aches, often preceded by diarrhea or other gastrointestinal symptoms).
- 4. \(\geq \) Grade 3 flu-like symptoms or cytokine release symptoms that persist for >24 hours after study treatment administration despite symptomatic treatment.

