11.6.1 Treatment Modification Guidelines

The dose of ADXS11-001 will not be modified (e.g., reduced or increased). However, treatment may be delayed or discontinued for drug related severe and life-threating toxicities, as shown below in Table 11.

Table 11 Treatment Delay/Discontinuation Guidelines for Drug-Related Adverse Events

Toxicity	Grade	Hold treatment	Timing for restarting treatment	Discontinue Treatment
	1,2,3	No	N/A	N/A
Hematologic	4	Yes	Toxicity resolves to ≤Grade 1 or baseline	Toxicity does not resolve to ≤Grade 1 or baseline within 12 weeks
	1	No	N/A	N/A
Non- hematologic, excluding cytokine release symptoms and DLTs	2-3	Yes	Toxicity resolves to ≤Grade 1	Toxicity not resolved to ≤Grade 1 within 12 weeks of last infusion ^a
	4	N/A	Permanent treatment discontinuation	Permanent Discontinuation from Treatment

^a With investigator and sponsor agreement, subjects with a non-hematologic AE (e.g. alopecia, neuropathy) still at grade 2 after 12 weeks, may continue treatment if only asymptomatic and controlled.

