11.6.2 ADXS11-001 Treatment Alterations

Subjects who experience a DLT during the dose escalation portion of the study or experience events described as a DLT in any subsequent treatment cycle will be discontinued from study treatment. However, if the subject who experienced a DLT shows significant response to ADXS11-001, they may be eligible to receive ADXS11-001 at a lower dose level for subsequent doses and cycles following discussion and agreement between the Investigator and Sponsor. See Section 6.1 Dose Limiting Toxicity Criteria for definition of DLT.

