14.5 Study Populations

All subjects who receive at least 1 dose of study treatment will be included in the safety analyses. All subjects who complete at least 1 cycle of ADXS11-001 treatment will be included in the efficacy population.

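### The rule that stops treatment after a DLT-type event does not plainly reach expansion cycle 1 or Days 29–84 of escalation cycle 1, and Tables 9 and 11 give other outcomes there

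*Combined protocol and SAP*

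**What the plan says.** - **Stopping rule.** Section 6 discontinues treatment for a DLT in dose escalation, and also for subjects who "experience events described as a DLT in any subsequent treatment cycle will be discontinued from study treatment". Section 11.6.2 repeats the rule: "Subjects who experience a DLT during the dose escalation portion of the study or experience events described as a DLT in any subsequent treatment cycle". Both sections let a responder continue at a lower dose level if the investigator and sponsor agree, and both refer to Section 6.1 for the definition of a DLT.
- **DLT window.** Section 6: "DLTs will only be assessed during the first 28 days in cycle 1". Section 6.1: "DLT will be evaluated during the first 28 days of the first cycle during the dose escalation portion of the trial". The Synopsis differs: DLTs are "assessed during the first treatment cycle, the dose will be escalated to the next dose level for the next 3 subjects".
- **Cycle.** Infusions are given "on Day 1 of Weeks 1, 4, 7, and 10 of each 12-week cycle".
- **Treatment modification.** Section 6.1 refers the reader to Table 11 (Section 11.6.1) for the handling of DLTs. Table 11's non-hematologic row is labelled as "excluding cytokine release symptoms and DLTs"; its hematologic row has no such exclusion. Cytokine release symptoms are handled in Table 9 (Section 11.4.1).

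**The concern.** The stopping rule has two limbs: a DLT in escalation, and a DLT-type event in a later cycle. If a DLT can exist only on Days 1–28 of escalation cycle 1, two stretches of treatment belong to neither limb: the rest of cycle 1 for escalation subjects, and all of cycle 1 for expansion subjects. A site facing a related Grade 3 event there would turn to Tables 9 and 11, which do not give the same answer as the stopping rule. Re-dosing after the same event could then depend on the day and the study portion, in a trial whose primary objective is safety and tolerability.

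**Working it through.** The plan states no figure to reproduce. The check maps the schedule onto the two limbs, then reads off what the tables say in the uncovered part.

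**Coverage**

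1. Infusion day = (week − 1) × 7 + 1. Weeks 1, 4, 7 and 10 give nominal Days 1, 22, 43 and 64 of an 84-day cycle.
2. Escalation, 28-day window: 84 − 28 = 56 days uncovered, and 56/84 = 67%. Infusions 3 and 4 (Days 43 and 64) lie wholly outside. Infusion 2 is followed inside the window on Days 22–28 only. With the ±7-day allowance in the Table 5 footnotes, infusion 2 can fall anywhere on Days 15–29, so possibly outside the window itself.
3. Escalation, Synopsis window (first cycle): 0 of 84 days uncovered.
4. Expansion, either window: 84 of 84 days and 4 of 4 infusions uncovered, because Section 6.1 confines DLTs to escalation and cycle 1 is not a later cycle.
5. Upper limits on infusions, if every subject completes cycle 1: escalation, 2 × (6 to 12 subjects, Section 14.3) = 12–24. For expansion, about 15 subjects at the RP2D less 3–6 already treated there leaves 9–12, so 4 × (9 to 12) = 36–48. The expansion cohort is optional.

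**Outcome for a related event that meets Section 6.1**

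| Event | Stopping rule (Sections 6, 11.6.2) | Tables 9 and 11 |
|---|---|---|
| Grade 3 non-hematologic | Discontinue | Hold, restart once resolved to Grade 1 or less; no rule if the word DLTs in Table 11 means DLT-type events at any time |
| Grade 3 thrombocytopenia lasting more than 72 hours | Discontinue | Not held |
| Grade 4 hematologic | Discontinue | Hold and restart; discontinue only if unresolved at 12 weeks |
| Grade 3 cytokine release symptoms persisting beyond 24 hours, other than hypotension | Discontinue | Longer infusion, with more prophylaxis considered |
| Grade 3 hypotension as a cytokine release symptom, persisting beyond 24 hours | Discontinue | Discussion with the sponsor |
| Grade 4 non-hematologic, or Grade 4 hypotension/organ toxicity | Discontinue | Permanent discontinuation |

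The exception for responders qualifies every entry in the middle column. As an example, take a related Grade 3 non-hematologic event in an escalation subject under the 28-day window. It leads to discontinuation on Day 20, to hold-and-restart or no rule on Day 50, and to discontinuation again on Day 90 (cycle 2).

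**Days 1–28 are not settled either.** Section 6.1 sends DLTs to Table 11. For a Grade 4 hematologic DLT on Day 20, Section 6 says discontinue, while Table 11's hematologic row says hold and restart. For non-hematologic DLTs the same cross-reference leads to a row that excludes them.

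**Illustration only.** The documents as provided give no rate of DLT-type events per infusion. Assume 2%, 5% or 10%, with infusions independent and all given. The chance of at least one event, 1 − (1 − p)^n, is then 21.5–38.4%, 46.0–70.8% or 71.8–92.0% for n = 12–24 (escalation), and 51.7–62.1%, 84.2–91.5% or 97.7–99.4% for n = 36–48 (expansion). Some of these would be Grade 4 non-hematologic events, for which the two rules agree.

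**The case against.** The strongest reply is that the gap depends on how the rule is read.

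- The stopping sentence itself carries no 28-day limit, and the Synopsis assesses DLTs over the first cycle. On that text a Day 50 event in escalation is a DLT and the first limb covers it. This stands as a possible reading. But the same paragraph refers to Section 6.1 for the definition, and Sections 6 and 6.1 both state 28 days. The reading therefore closes half the gap only by relying on a contradiction.
- The second limb may be meant to carry the Section 6.1 criteria past the counting window, with a subsequent cycle meaning any cycle after escalation. That would take in expansion cycle 1. The text does not say so. The next sentence distinguishes later doses from later cycles, which favours the ordinary meaning of cycle 2 onward.
- Investigators can withdraw a subject (Section 11.8.1) and must find laboratory results acceptable before each dose (Section 13.8). This is a real safeguard, but it is discretion and does not say which rule applies.

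A reader might also infer more than the documents support:

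- **That toxicity discontinuations and exposure can no longer be compared between escalation and expansion.** No such comparison is planned. Analyses are descriptive, with AEs summarised by dose (Section 14.5.4).
- **That the gap distorts the efficacy denominator.** That effect comes from the completer definition, "All subjects who complete at least 1 cycle of ADXS11-001 treatment will be included in the efficacy population", whatever the reason for stopping; a Day 20 discontinuation leaves that population too. The Synopsis also tabulates response for all treated subjects.
- **That one uniform outcome across all periods is required.** Nothing in the documents demands it, and it would be a clinical choice.

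**Conclusion.** The concern holds as a conflict in the text that bears on re-dosing. No passage expressly applies the stopping rule to expansion cycle 1. Under the 28-day window, none applies it to Days 29–84 of escalation cycle 1 (56 of 84 days, nominal infusions 3 and 4). The expansion gap does not depend on which DLT window is used, but it does rest on reading a subsequent cycle as cycle 2 onward. The escalation gap rests on Sections 6 and 6.1 prevailing over the Synopsis. The outcome differs for Grade 3 non-hematologic events, prolonged Grade 3 thrombocytopenia, Grade 4 hematologic toxicity and persistent Grade 3 cytokine release symptoms. It does not differ for Grade 4 non-hematologic events, apart from the exception for responders. For hematologic DLTs the conflict is already present within Days 1–28. The infusion counts are upper limits on exposure under an unclear rule and do not predict events; the conclusion does not rely on the assumed rates.

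**What to change.** Reconcile the Synopsis, Section 6, Section 6.1, Table 9, Section 11.6.1 with Table 11, and Section 11.6.2, so that:

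1. the window used to count DLTs for dose decisions is stated once, separately from the treatment rule for events meeting the Section 6.1 criteria;
2. the text says which treatment rule applies on Days 1–28, on Days 29–84, in later cycles and in expansion cycle 1;
3. that rule agrees with Tables 9 and 11, including what the word DLTs covers in Table 11's non-hematologic row and how its hematologic row relates to Section 6.

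The same edit should square the statement in Section 11.6.1 that the dose is not modified with the lower-dose exception in Sections 6 and 11.6.2. The clinical outcome in each period is for the sponsor to decide.

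In Section 14.5.4, add a table by dose of events meeting the Section 6.1 criteria, whenever they occur, using the grade, causality and dates already collected. The cost is wording in these places and one table, with no extra subjects, visits or data items.

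### As the visible text stands, a recommended Phase 2 dose (RP2D) can be named on 0 DLTs in 3 subjects, because going on to 6 is then only a sponsor option

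*Combined protocol and SAP*

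**What the plan says.** The Synopsis (Methodology) treats 3 subjects per level and gives one trigger for more: "If DLT is seen in 1 of 3 subjects, another 3 subjects will be treated at that same dose". Two DLTs in 6 fails the level, "and the previous dose level will be selected as the recommended Phase 2 dose (RP2D"). The selection criterion is "The RP2D will be selected based on an observed DLT rate of < 33" per cent.

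Section 6 agrees. Cohort size is flexible: "ADXS11-001 will be administered in sequential cohorts of 3-6 subjects". At the first level, "If no DLTs are experienced in the 28 day DLT observation period at Dose Level 1, the next dose level" is explored. For the second level the written trigger is again a DLT: "If 1 DLT is experienced at Dose Level 2", 3 more are enrolled, and 1 DLT in 6 allows that level to be the RP2D. No visible sentence covers Dose Level 2 at 0/3. None brings Dose Level 1 up to 6 if the trial returns to it. The remaining route from 3 to 6 is the sponsor's reserved right ("The Sponsor reserves the right to expand the number of subjects in each of the cohorts to better evaluate safety and tolerability"), with the increment fixed but no trigger: "Cohorts will be expanded in groups of 3 subjects".

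Section 14.3 plans 6 to 12 escalation subjects. After the RP2D is identified, an optional expansion brings that level to about 15, and its subjects may all enrol at once (Section 6). Section 6.1 ties DLT evaluation to the escalation portion. Section 14.6 plans no formal interim analysis.

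**The concern.** Safety and tolerability is the only primary objective, and the RP2D is the dose carried into the expansion. Two routes name it on 3 subjects. In the first, Dose Level 2 shows 0/3, and 0% meets the criterion. In the second, Dose Level 2 fails and the choice falls back to Dose Level 1, which will usually have had only 3 subjects because a clean 3 sends the trial straight up.

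About 12 more subjects (15 − 3) could then start together on a dose backed by 0/3, with no DLT boundary in the expansion that would reverse the choice.

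**Working it through.** **Inputs.** From the Synopsis and Section 6: 3 per level; 1/3 adds 3; 0/3 or 1/6 passes; 2/6 fails (2/6 = 33.3% is not below 33%). From Section 14.3: 6 to 12 escalation subjects. The visible text gives no true DLT rate, so a range of 10% to 50% is assumed. Further assumptions: DLTs are independent, 2 or more in the first 3 fails any level, and 1/6 at Dose Level 1 escalates.

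**Step 1: the plan's own figure.** Under the written rules, a trial that names an RP2D visits two levels (1 then 2, or 1 then −1) with 3 or 6 subjects at each. The minimum is 3 + 3 = 6 and the maximum 6 + 6 = 12, which reproduces 6 to 12. If 6 were mandatory at the RP2D, the minimum would be 3 + 6 = 9. The planned minimum therefore favours the reading that 3 can suffice. It is supporting evidence only: Dose Level −1 is optional, so a trial that fails Dose Level 1 could stop after 3 subjects.

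**Step 2: one level, given that it is tested.** Let p be the true DLT rate and q = 1 − p.

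- Option never used at 0/3: A = q³ + 3pq²·q³
- Six subjects at 0/3, at most 1 DLT in 6: B = q⁶ + 6pq⁵
- Difference: A − B = q³ × P(2 or more DLTs in the next 3)

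At p = 1/3, q³ = 0.2963. A = 0.2963 + 0.4444 × 0.2963 = 0.4280. B = 0.0878 + 0.2634 = 0.3512. The difference is 0.2963 × 0.2593 = 0.0768. Of the acceptances under A, 0.2963/0.4280 = 69% rest on 0/3.

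| True rate | A: never used | B: six subjects | Difference (points, before rounding) |
|---|---|---|---|
| 10% | 90.6% | 88.6% | 2.0 |
| 20% | 70.9% | 65.5% | 5.3 |
| 25% | 60.0% | 53.4% | 6.6 |
| 33.3% | 42.8% | 35.1% | 7.7 |
| 40% | 30.9% | 23.3% | 7.6 |
| 50% | 17.2% | 10.9% | 6.3 |

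These are conditional on the level being reached. For Dose Level 2 they are multiplied by the chance of passing Dose Level 1. With a true 10% there, 0.9061 × 0.4280 = 38.8% and 0.9061 × 0.3512 = 31.8%.

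**Step 3: Dose Levels 1 and 2 together, leaving out Dose Level −1.** The share of named RP2Ds resting on 3 subjects, option unused, is [A(p₁)q₂³ + q₁³(1 − A(p₂))] / A(p₁).

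- 10%/25%: (0.3823 + 0.2917)/0.9061 = 74%
- 20%/33.3%: (0.2100 + 0.2929)/0.7086 = 71%
- 25%/40%: (0.1296 + 0.2914)/0.5999 = 70%

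**Step 4: what 3 or 6 subjects show.** Exact 95% intervals are 0 to 70.8% for 0/3, 0 to 45.9% for 0/6, and 0.4 to 64.1% for 1/6. All three include 33%. Six subjects narrow the uncertainty but do not settle it.

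**The case against.** The strongest reply is that requiring 6 mostly makes the rule stricter and hardly improves discrimination. The gap in acceptance between a true 25% and a true 33.3% dose moves only from 17.2 points (60.0 − 42.8) to 18.3 (53.4 − 35.1). The 6.6-point loss at 25%, a rate the plan would want to accept, nearly matches the 7.7-point gain at 33.3%. This stands, and it belongs in the stated costs.

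A reader might take 42.8% as the plan's chance of recommending a dose that is too toxic. The documents do not support that. The figure applies to a level that is tested, with the sponsor's option never used at 0/3, and no visible text suggests that the true rate is 33.3%. Sections 3.4.1.1 and 10.2.1 report that 1 × 10¹⁰ CFU was given in an earlier Phase 1 study. Section 11.4.1 puts Grade 3–4 hypotension at about 1%. The safety tables are not visible. None of this supplies a DLT rate in either direction.

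A reader might also infer that the plan rules out 6 subjects, or that the expansion is unmonitored. Neither follows. Section 6 calls the design standard 3 + 3 and points to Figure 1, which is not shown and may hold a branch that the bullets lack. Adverse events are monitored (Section 14.6), a Grade 4 event may suspend the study (Section 11.8.2), and a subject with a DLT-type event comes off treatment, with a lower dose possible for a responder (Sections 6 and 11.6.2). These are real protections, but none is a rule that revisits the RP2D. If Figure 1 does require 6, the Synopsis omits it and the two should be aligned.

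**Conclusion.** The point holds in a limited form. On the visible text, 0/3 is enough to name an RP2D, and in the illustrated two-level scenarios that is the usual basis (70% to 74%) if the sponsor does not enlarge a clean cohort. At an illustrative true rate of 33.3%, a tested level is accepted between 35.1% and 42.8% of the time, depending on how often the option is used.

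The case for change rests less on the 7.7 points than on sequence: an optional step would become a condition met before the remaining expansion subjects enrol. This is a worthwhile clarification of the selection rule. It does not show that the design is unsafe. It depends on the assumed rates, on independent DLTs, and on Figure 1 adding no further rule.

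**What to change.** State in Section 6 and the Synopsis that a level standing at 0/3 when it is about to be named RP2D takes 3 more subjects. They complete the 28-day DLT period, with at most 1 DLT in 6, before the remaining expansion subjects enrol, and they count toward the approximately 15. If Dose Level 1 then shows 2 or more DLTs in 6, it is not the RP2D and the existing Dose Level −1 option applies.

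Costs to state:

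- **Subjects.** None extra if the expansion opens; 3 if it does not.
- **Time.** About 28 days plus accrual of 3.
- **Escalation size.** The minimum for a named RP2D rises from 6 to 9, so the Synopsis and Section 14.3 need amending. The total can exceed 12 in one uncommon branch: Dose Level 1 at 0/3, Dose Level 2 fails, Dose Level 1 fails on re-expansion, and Dose Level −1 opens. If Dose Level −1 is then named on 6, the total is 6 + 3 + 6 = 15 or 6 + 6 + 6 = 18. With true rates of 33.3%/50%, Dose Level 1 fails in this way with probability 0.2963 × 0.8906 × 0.2593 = 6.8%.
- **Acceptable doses turned down.** True 10%: 9.4% to 11.4%. True 20%: 29.1% to 34.5%. True 25%: 40.0% to 46.6%. These compare the option never used with 6 required; if the sponsor would always have used it, the rates do not change.
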